3.3 Patient disposition, demographics and other baseline characteristics

The Full Analysis Set (FAS) will be used for all baseline and demographic summaries and listings unless otherwise specified. Summaries will be reported by age group (defined in [Table 1-1](#)) and for all patients and listings will be reported by age group to assess baseline comparability. If more than one dose group are assigned under one age group, summaries and listings will be reported by both age group and dose group. No inferential statistics will be provided.

Basic demographic and background data

All demographic and baseline disease characteristics data will be summarized and listed by age group and for all patients. Categorical data (e.g. gender, race, ethnicity) will be summarized by frequency counts and percentages; the number and percentage of patients with missing data will be provided. Continuous data (e.g. age, weight, height, body surface area, body mass index) will be summarized by descriptive statistics (N, mean, median, standard deviation, minimum and maximum).

Diagnosis and extent of disease

Summary statistics will be tabulated for diagnosis, overall aGvHD grade at diagnosis/baseline and stem cell transplant type.

For underlying disease, the analysis will include the following: primary diagnosis classification, details of primary diagnosis, time from diagnosis of underlying disease to start of study treatment, CIBMTR risk assessment.

For transplant related disease history, the analysis will include the following: conditioning regimen type, total HCT-specific comorbidity index score, time from transplant to the start of study treatment, time from diagnosis of underlying disease to transplant, stem cell type, cytomegalovirus status, time from engraftment to start of study treatment, time from transplant to engraftment, donor information including age, gender, HLA typing method, HLA match score, source of grafts, CMV status, T-cell depleted (Y/N), total nucleated cell dose.

For aGvHD disease history, the analysis will include the following: time from diagnosis of aGvHD to start of study treatment, Overall aGvHD grade when diagnosis of aGvHD, steroid refractory aGvHD criteria met, prior aGvHD therapy (steroid only, steroid + CNI, missing), time from diagnosis of aGvHD to steroid refractory, time from steroid refractory aGvHD to start of study treatment, Overall aGvHD grade when diagnosis of SR aGvHD, and aGvHD organ involvement.

Medical history

Medical history and ongoing conditions, including underlying disease conditions and symptoms entered on eCRF will be summarized and listed by age group and for all patients. The summaries will be presented by primary system organ class (SOC), preferred term (PT) and group. Medical history and current medical conditions will be coded using the Medical Dictionary for Regulatory Activities (MedDRA) terminology. The MedDRA version used for reporting will be specified in the CSR and as a footnote in the applicable tables/listings.

3.3.1 Patient disposition

Enrollment by country and center will be summarized for all screened patients and also by age group and for all patients. The number (%) of treated patients will be presented overall and by age group. The number (%) of screened and not-treated patients and the reasons for screening failure will also be displayed. The number (%) of patients in the FAS who are still on treatment, who discontinued the treatment and the study as well as the reason for discontinuation, will be presented overall and by age group.

Protocol deviations

The number (%) of patients in the FAS with any protocol deviation will be tabulated by deviation category overall and by age group for the FAS. All protocol deviations will be listed.

To assess the impact of COVID-19 pandemic on the conduct of the study, COVID-19 specific protocol deviations will be listed separately.

Analysis sets

The number (%) of patients in each analysis set (defined in [Section 2.2](#)) will be summarized by age group.

3.4 Treatments (study treatment, rescue medication, concomitant therapies, compliance)

3.4.1 Study treatment / compliance

Duration of exposure in days to ruxolitinib will be summarized by age group and by means of descriptive statistics. It will also be categorized into time intervals; frequency counts and percentages will be presented for the number (%) of patients in each interval.

Total daily dose, actual cumulative dose, dose intensity (DI) and relative dose intensity (RDI) will be summarized for ruxolitinib by age group.

The number (%) of patients who have dose reductions or interruptions, and the reasons, will be summarized for ruxolitinib by age group.

Patient level listings of all doses administered on treatment along with dose change reasons will be produced by age group.

The Safety Set will be used for all summaries and listings of study treatment.

If more than one dose and/or formulation is assigned within one age group, then summaries and listings will be reported by age group as well as doses/formulations within the age group.

Duration of exposure to study treatment

Duration of exposure to study treatment (days) = (last date of exposure to study treatment) – (date of first administration of study treatment) + 1.

Summary of duration of exposure of study treatment in days will include categorical summaries (based on clinically meaningful time intervals) and continuous summaries (i.e. mean, standard deviation etc.) using appropriate units of time.

Duration of exposure in patient-years

The duration of exposure in patient-years is a total of the duration of exposure in years from all the patients in the agegroup.

Duration of exposure to systemic corticosteroid

Duration of exposure to systemic corticosteroid treatment (days) = (last date of exposure to systemic corticosteroid) – (date of first administration of systemic corticosteroid) + 1.

Duration of exposure to systemic corticosteroid in patient-years

The duration of exposure to systemic corticosteroid in patient-years is a total of the duration of exposure to systemic corticosteroid in years from all the patients in the age group.

Duration of exposure to CNIs

Duration of exposure to CNI treatment (days) = (last date of exposure to CNI) – (date of first administration of CNI) + 1.

Duration of exposure to CNI in patient (years)

The duration of exposure to CNI in patient-years is a total of the duration of exposure to CNI in years from all the patients in the age group.

Cumulative dose

The **planned cumulative dose** for ruxolitinib refers to the total planned dose as per protocol for each group up to the last dose date.

The **actual cumulative dose of ruxolitinib** refers to the total actual dose of ruxolitinib as documented in the Study Treatment eCRF.

For patients who did not take any drug the cumulative dose is by definition equal to zero.

Dose intensity and relative dose intensity of ruxolitinib

Subjects receive ruxolitinib in doses twice a day (bid). For purposes of reporting dose intensity, a summary of dose per day (total daily dose) is provided.

Dose intensity (DI) of ruxolitinib for patients with non-zero duration of exposure is defined as follows:

DI (mg / day or mg/m²/day) = Actual cumulative dose (mg or mg/m²) of ruxolitinib / Duration of exposure to ruxolitinib (days).

For patients who did not take any drug the DI is by definition equal to zero.

Planned dose intensity (PDI) is defined as follows:

PDI (mg / day or mg/m²/day) = Planned Cumulative dose (mg or mg/m²) / Duration of exposure (days).

The PDI of ruxolitinib with daily dose schedule is according to protocol for the three age groups:

- Age group 1: 20 mg/day
- Age group 2: 10 mg/day
- Age group 3: 8 mg/m²/day using the baseline BSA

Relative dose intensity (RDI) is defined as follows:

RDI = DI (mg / day or mg/m²/day) / PDI (mg / day or mg/m²/day).

The total daily dose, actual cumulative dose, DI and RDI up to last date of exposure to study treatment will be summarized.

Dose reductions, interruptions or permanent discontinuations

The number of patients who have dose reduction, or interruptions, and the reasons, will be summarized for ruxolitinib by age group. Number of patients with dose change due to dose tapering (change of dose due to efficacy of treatment) and patients with dose change due to

other reasons (potential safety concerns) will be summarised. The number of patients who have dose permanent discontinuations and the reasons will be summarized by age group.

‘Type of change’ and ‘Dose permanently discontinued’ fields from the Study Treatment CRF pages will be used to determine the dose change, dose interruptions, and permanent discontinuations respectively.

The corresponding fields ‘Reason for Change’ and ‘Reason for Permanent Discontinuation’ will be used to summarize the reasons.

For the purpose of summarizing interruptions and reasons, in case multiple entries for interruption that are entered on consecutive days with different reasons will be counted as separate interruptions. However, if the reason is the same in this mentioned multiple entries on consecutive days, then it will be counted as one interruption.

Dose Reduction: A dose change when the actual total daily dose is lower than the previous actual total daily dose. Any dose change due to dose tapering (change of dose due to efficacy of treatment) will not be considered as a dose reduction. Only dose changes that are indicated on the CRF due to reason other than dose tapering are taken into consideration. Number of reductions will be derived programmatically based on the change and the direction of the change.

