Patients should be instructed not to take study treatment at home on the days of the scheduled pre-dose blood collection [REDACTED] [REDACTED]. Dosing will be administered after pre-dose blood collection at these visits.

At each study visit **after Day 56**, the Investigator may consider a ruxolitinib dose change based on the patient's current age and/or BSA. At the Investigator's discretion, dosing may be adjusted if the newly calculated dose (based on the patient's current age and/or BSA) is a >10% change from the current dose.

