6.1.5.1 Tapering Guidelines

Tapering of immunosuppression will follow 2 steps: first taper of corticosteroids, followed with taper of CNI and/or ruxolitinib in responding patients. If applicable, the taper of CNI and ruxolitinib may be performed at the same time.

During the Treatment Period, immunosuppression taper guidelines are:

1. **Corticosteroids:** the taper of corticosteroids in patients demonstrating a PR or CR as observed by the Investigator must not be initiated earlier than Day 7, and should then be performed per institutional guidelines (e.g. 10% dose reduction every 5 days, beginning no earlier than Day 7 and continuing to approximately Day 56 to allow 7-8 week taper).
2. **CNI (cyclosporine or tacrolimus):** CNI taper is allowed in patients demonstrating a PR or CR, once off corticosteroids, and should then be performed per institutional guidelines (e.g. 25% dose reduction per month).
3. **Ruxolitinib:** ruxolitinib taper is allowed in patients demonstrating a PR or CR, once off corticosteroids, and must not start earlier than Day 56.

The following guidance may be followed based on evaluation of the condition of the patient, current dosing regimen and the clinical judgment of the Investigator: a 50% dose reduction every 2 months (approximately every 56 days), i.e., initial dose reduction from 10 mg BID to 5 mg BID and, if sustained aGvHD stable disease is observed, patient is further tapered by a second 50% dosage reduction to 5 mg QD for an additional 56 days, prior to cessation. No further reductions will be allowed beyond once a day dose. Refer to [Table 6-4](#).

It is expected that the taper of corticosteroids, CNI, and ruxolitinib will be completed by the end of Week 24. Should an aGvHD flare or other safety concern prevent taper from being complete by then, the dose of ruxolitinib may be maintained until Week 24. Ruxolitinib taper completion will be consequently delayed beyond Week 24, but must be complete by Week 48 maximum.

All patients **must** be off corticosteroids, CNIs and ruxolitinib by the Week 48 maximum.

6.1.5.1.1 aGvHD flare

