3.2 Analysis sets

If the starting dose is different from the assigned dose level due to co-administration of ruxolitinib with strong CYP3A4 or dual CYP3A4/CYP2C9 inhibitors, these patients will be included under the assigned dose level and considered that they have received the full assigned dose. This applies to all analysis sets described below.

The **Full Analysis Set** (FAS) comprises all patients to whom study treatment has been assigned and who received at least one dose of study treatment. Patients will be analyzed according to the treatment they have been assigned to.

The **Safety Set** includes all patients who received at least one dose of study treatment. Patients will be analyzed according to the study treatment received, where treatment received is defined as the assigned dose level of ruxolitinib if the patient took at least one dose of that treatment or the first dose level received if the assigned dose level was never received.

The **Pharmacokinetic Analysis Set** (PAS) includes all patients who provide at least one evaluable PK concentration. For a concentration to be evaluable, patients are required to:

- Take the dose of ruxolitinib prior to PK sample.
- For pre-dose samples, do not vomit within 2 hours after the previous dosing of ruxolitinib prior to sampling; for post-dose samples, do not vomit within 2 hours after the dosing of ruxolitinib.

The PAS will be used for Non-compartmental analysis (NCA) for patients where extensive PK sampling is obtained. This analysis set will also be used for any exposure-response analysis

The **Efficacy Eevaluable Set** (EES) comprises all patients to whom study treatment has been assigned at the Recommended Phase 2 dose (RP2D) of ruxolitinib and who received at least one dose of study treatment at that dose level. If the starting dose is different from the RP2D due to co-administration of ruxolitinib with strong CYP3A4 or dual CYP3A4/CYP2C9 inhibitors, these patients will be included in the EES.

All statistical analysis and data presentation for all analysis sets will exclude any data collected but not required as per study protocol. Data with a Protocol Deviation Code OTH11 (Other GCP deviation- Additional samples or Data collected not required as per protocol) will not be part of the analysis data or any output presentation.

Any patients who withdrew Informed Consent or from whom written Informed Consent was not obtained (Protocol Deviation INCL01) will be excluded from all analyses sets.

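### Ruxolitinib relative dose intensity counts permitted efficacy tapering as under-dosing, so it cannot tell a planned taper from a toxicity reduction

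*SAP*

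**What the plan says.** SAP 3.4.1 builds the ruxolitinib exposure summary as follows.

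- Planned cumulative dose "refers to the total planned dose as per protocol for each group up to the last dose date".
- Planned dose intensity (PDI) is planned cumulative dose divided by duration of exposure. The SAP then supplies the values: "The PDI of ruxolitinib with daily dose schedule is according to protocol for the three age groups". They are "Age group 1: 20 mg/day", "Age group 2: 10 mg/day" and "Age group 3: 8 mg/m²/day using the baseline BSA".
- Dose intensity (DI) is actual cumulative dose divided by duration of exposure, and RDI is DI/PDI. Both are summarised to the last date of exposure.
- Patients with taper changes are counted separately from patients with other dose changes, and a taper step is not counted as a dose reduction.

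Protocol 6.1.5.1 lets patients in PR or CR who are off corticosteroids taper ruxolitinib from Day 56 at the earliest. Its example schedule is "a 50% dose reduction every 2 months (approximately every 56 days"), going from 10 mg BID to 5 mg BID to 5 mg QD for a further 56 days and then stopping. The schedule is guidance. Completion is expected by the end of Week 24, with Week 48 as the limit. Protocol Table 6-4 gives a second reduction step only for the Group 1 starting dose.

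Two neighbouring rules also bear on the denominator. SAP 3.2 says that patients started on a different dose because of a strong CYP3A4 or dual CYP3A4/CYP2C9 inhibitor are "considered that they have received the full assigned dose". Protocol 6.1.1 says that, after Day 56, "dosing may be adjusted if the newly calculated dose" differs from the current one by more than 10%.

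**The concern.** The text and the constants in SAP 3.4.1 do not match. Planned dose is said to follow the protocol, and the protocol provides for tapering in responders. The listed constants are the starting dose held to the end of exposure. Tapered days therefore enter the numerator at the reduced dose and the denominator at the full dose.

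A low RDI is normally read as poor tolerability or missed drug. Here it can also mean that the patient responded, came off steroids and was tapered as the protocol foresees, and the summary gives no way to tell which. It also conflicts with the SAP's own treatment of dose changes: a patient with no dose reductions in one table can show an RDI well below 100% in the next.

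**Working it through.** **Inputs.** Starting doses of 10 mg BID, 5 mg BID and 4 mg/m² BID (Protocol Table 6-1). PDI constants and the RDI formula (SAP 3.4.1). Taper timing and steps (Protocol 6.1.5.1). Number of reduction steps by group (Protocol Table 6-4).

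**Step 1: reproduce the PDI constants.** Twice the BID starting dose gives 2 × 10 = 20 mg/day, 2 × 5 = 10 mg/day and 2 × 4 = 8 mg/m²/day. All three match the SAP, so the constants contain no taper.

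**Step 2: RDI under the SAP definition.** RDI = (sum of daily dose × days) / (days of exposure × PDI).

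| Patient | Calculation | RDI |
|---|---|---|
| Group 1, example taper, full dose through Day 56, stop at Day 168 | (56×20 + 56×10 + 56×5) / (168×20) = 1960/3360 | 58.3% |
| Same, first reduced dose on Day 56 itself | (55×20 + 56×10 + 57×5) / (168×20) = 1945/3360 | 57.9% |
| Group 2, one step, reduced dose for 56 days | (56×10 + 56×5) / (112×10) = 840/1120 | 75.0% |
| Group 2, one step, reduced dose held to Week 24 | (56×10 + 112×5) / (168×10) = 1120/1680 | 66.7% |
| Group 3, one step, 56 days | (56×8 + 56×4) / (112×8) = 672/896 | 75.0% |
| Group 3, one step, held to Week 24 | (56×8 + 112×4) / (168×8) = 896/1344 | 66.7% |
| Group 1, taper starts after Day 168 | (168×20 + 56×10 + 56×5) / (280×20) = 4200/5600 | 75.0% |
| Group 1, taper starts after Day 224, ends Week 48 | (224×20 + 56×10 + 56×5) / (336×20) = 5320/6720 | 79.2% |

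**Step 3: comparison patients.**

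| Patient | Calculation | RDI |
|---|---|---|
| Group 1, halved for toxicity after Day 28, kept there to Day 168 | (28×20 + 140×10) / (168×20) = 1960/3360 | 58.3% |
| Group 1, full dose, stopped at Day 28 for lack of response | (28×20) / (28×20) = 560/560 | 100% |

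The tapering patient and the toxicity patient have the same cumulative dose (1960 mg), the same duration and the same RDI.

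**Step 4: the same two patients under a taper-free window.** With RDI cut the day before the first taper-coded change, the tapering patient has 1120/1120 = 100%. The toxicity patient has no taper-coded change and stays at 58.3%. With RDI to Day 56, the tapering patient has 100% (full dose through Day 56) and the toxicity patient (28×20 + 28×10) / (56×20) = 840/1120 = 75%. Either window separates them.

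**The case against.** The strongest reply is that RDI carries little weight here and the SAP already separates tapering elsewhere. Protocol 12.3 plans dose intensity and does not mention RDI. Protocol 12.5.2 measures tolerability by counts of dose increases, reductions and interruptions. Protocol 6.6.1 has compliance assessed at each visit and verified by plasma ruxolitinib. Taper changes are summarised separately, all doses are listed with reasons, and the constants are openly stated. The taper is also individualised, so the starting dose is the one denominator that can be fixed in advance. All of this stands and limits the point to a descriptive table. It does not remove the inconsistency between that table and the dose-reduction rule.

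Three stronger readings are tempting, and the documents do not support them.

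- A reader might infer that RDI is lowest in responders and so reverses its meaning. The toxicity example gives exactly the same 58.3%. A patient kept at half dose throughout for an inhibitor would be near 50%, which is lower. The supportable statement is that RDI is lowered in responders who taper and mixes two causes.
- A reader might infer a built-in false association between low dose intensity and response. SAP 3.10 names dose intensity, not RDI, and only as an optional alternative measure. The trough averages it specifies for the response models stop at Day 28 and Day 56, and tapering cannot begin before Day 56. The problem would arise only if whole-period dose intensity were used for those responses; the SAP leaves that window open.
- A reader might infer that the inhibitor rule in SAP 3.2 or the baseline-BSA denominator contradicts the RDI definition. The first governs how patients are classified in the analysis sets, not the milligrams reported. The second is an explicit choice, and later dose recalculation is at the investigator's discretion. Both are defensible.

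**Conclusion.** The point holds as an inconsistency in a secondary exposure summary. As defined, ruxolitinib RDI counts permitted efficacy tapering as under-dosing and cannot separate it from a reduction for intolerance. It also disagrees with the SAP's exclusion of tapering from dose reductions.

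The size depends on group and timing. The 58.3% figure assumes Group 1, steroids already stopped, the earliest taper start, both steps of the example schedule and completion at Week 24. Groups 2 and 3 come out at about 67–75% under the single step in Table 6-4, and later Group 1 tapers at about 75–79%. Because the schedule is optional, these are values for patients who follow it, not a forecast for all responders.

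The Day 28 response rate and its confidence interval do not use RDI and are unaffected. RDI is not the trial's sole measure of compliance or tolerability. The correction is worth making because it is cheap and the present table is easy to misread.

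**What to change.** In SAP 3.4.1:

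1. Make the main ruxolitinib RDI the one computed from Day 1 to the earlier of the day before the first dose change coded as tapering and the last dose. The *Reason for Change* field on the study treatment CRF already identifies tapering.
2. Also report RDI to Day 28 and to Day 56, the early cut-offs that SAP 3.4.2.4 already uses for corticosteroids.
3. Keep the full-period RDI as a secondary row, labelled as including taper.
4. Leave the planned dose unchanged for inhibitor co-administration and for BSA or age changes. At most, add a footnote that RDI in these patients is relative to the unadjusted starting dose.

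In SAP 3.10, state that if dose intensity is used in the Day 28 or Day 56 response models, it is cut at that assessment day.

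The cost is SAP wording, one more summary and a little programming, with no new data and no change to any dosing rule. RDI to first taper omits toxicity changes that come after tapering starts; the retained full-period row and the dose-change tables still show them.

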3.4.2 Prior, concomitant and post therapies

3.4.2.1 Prior aGvHD therapy

The number and percentage of patients who received any prior aGvHD therapy will be summarized by lowest ATC class, preferred term and age group. Prior aGvHD procedures will be summarized by system organ class, preferred term and age group. The above analyses will be performed using the FAS. Data will also be listed.

